11.2 Determination of Sample Size

The results with the IMD and the RMD are collected on the same subject. SRTs are continuous and normally distributed data. We can therefore apply the sample size determination for mean difference

on one sample.

The formula to compute the sample size is:

$$n = \left(\frac{\sigma(z_{1-\alpha} + z_{1-\beta})}{\delta} \right)^2$$

With n the sample size, σ the standard deviation from the population, δ the non-inferiority margin, α the type I error, and $1-\beta$ the power of the test.

With the following input: $\sigma = 1.6$ dB SNR, $\delta = 1$ dB SNR, $\alpha = 0.05$, and $1-\beta = 0.8$, we will need a sample size of 16 to satisfy the test hypothesis.

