
Measurements and procedures:
	
Amplification is verified and compared with targets using Real Ear Measurements
 
Speech intelligibility is tested in background noise. Tests used include: Oldenburg Sentence Test (OLSA) and the Göttenburg Satztest (GÖSA). Speech tests are normally set up with speech in the front and noise at varying degrees around the participant. Tests such as the OLSA and GÖSA have a varying signal depending on the SNR goal.
 
Subjective perception of devices is tested with questionnaires asking the participants various questions concerning the expectations and benefits of the hearing devices. They can be given independently for the two different devices and then compared against one another.
 
Preference testing allows the participant to choose which hardware style that they prefer
 
Usability and handling is measured with in-house questionnaires that target the new hardware and possible handling difficulties

Study Product / Intervention:
	
Mermaid 9
 
The new investigational medical device (IMD) will be the Mermaid 9 ITE hearing device. The Mermaid 9 BTE device is already CE marked and sold on the market for almost one year. The only difference between the devices is the hardware which results in a different location of the microphone (in the ear versus behind the ear). Hearing instruments are worn approximately 8-10 hours per day and removed at night. The test participants will wear the new devices for a time period of 10 +/- 7 days. They will have already been wearing BTE devices for at least 6 months.
 
The IMD will be in a stable stage of development. This means that system testing will be complete to ensure correct implementation and safe behaviour of the devices before any testing on people is conducted. This also includes the software used to program the devices. The software will be at a stable stage of development.

Control Intervention (if applicable):
	
The reference devices are Mermaid 9 BTE hearing instruments.

Number of Participants with Rationale:
	
There will be an exploratory analysis of the data only. The total number of participants will be approximately 15-20.

Study Duration:
	
Approximately 1-2 months
 
The screening of the participants will begin in May 2018 and the final data collection appointments will occur in July 2018.

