6. STUDY DESIGN

6.1 General study design and justification of design

This is a controlled, randomized, open label, comparative clinical investigation conducted monocentric at the premises of Bernafon in Bern, Switzerland.

The exploratory study is based on a population of approximately 20 hearing impaired people that have a hearing loss appropriate for the IMD.

As an RMD, the subjects will be fit with Mermaid 9 BTEs during the trial. Additionally, a control situation will be the unaided test condition for speech testing.

There is no placebo or device that does not provide amplification. A single group assignment design is used with test subjects that have worn BTEs for approximately 6 months and will be fit with the RMD and IMD during the trial. The testing is unblinded as the main difference between the IMD and the RMD is hardware and therefore obvious to the end user that it's different.

A randomized test order will be used to test in a simulated environment. The test subjects will be tested using unaided and two aided conditions in a randomized manner for speech testing.

The participants are expected to participate for approximately 2-3 weeks for a combination of field and lab tests. There are two lab tests planned during which the participants will not spend more than 2 hours in the clinic (including breaks). The field test periods will not last more than 10 +/- 7 days.

The sequence will begin with the screening appointment in which participants are invited to the clinic for testing to determine if they are candidates for the trial. The entire test procedure will be explained, and they will be given a Patient Information and Informed Consent which will need to be signed, dated, and returned before any testing begins. If they choose to participate, a hearing test will be made to determine if they have an appropriate hearing loss, ear impressions will be made to make the custom fitting IMD, and the RMD will be fitted.

The following appointments will include fitting of the IMD, field tests during which they will wear the RMD and IMD, and lab tests in the clinic. There will be a total of 3 appointments, and each appointment will not exceed 2 hours. During the lab tests in the clinic they will participate in speech testing. Test subjects will be given questionnaires to complete at home and in the clinic.

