7.4 Criteria for withdrawal / discontinuation of participants

Participants are allowed to withdraw from the study at any time and for any reason. They do not have to share the reasons with the investigator. They will be asked to return the IMD. If the decision to withdraw is made by the investigator, the PI will inform the subject in person that they are no longer needed for the study. Reasons for withdrawing a participant from the study could be for non-compliance during testing, unreliable responses, medical reasons such as an ear infection, or the study may need to be stopped or postponed. Any data gathered from these subjects will be used for the current study. All data will remain encoded because results are only recorded using the identification code of the subject. There are normally at least five “back-up” test participants on the list to replace those that withdraw or are withdrawn. The “back-up” participants have already been screened and deemed to be appropriate for the study.

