11.1 Hypothesis

There is little evidence from research literature and experience that with equivalent technology, the IMD might be superior to the RMD for speech reception thresholds. Benefit from a more closed fit might be partially compensated by the larger distance between microphone on the BTE placement. However, we can expect that the performance should be at least as good with the IMD.

SRT benefit expressed in terms of benefit with amplification ($SRT_{unaided} - SRT_{aided}$), will be used as primary outcome in the following hypothesis and sample size calculation. As there is no technical motivation to find a benefit with the IMD, the tested hypothesis should therefore focus on the non-inferiority of the IMD compared to the RMD:

H0: average benefit with the IMD (μ_{IMD}) is not non-inferior to the average benefit with the RMD (μ_{RMD})

$$\mu_{IMD} \leq \mu_{RMD} - \delta$$

H1: average benefit with the IMD (μ_{IMD}) is non-inferior to the average benefit with the RMD (μ_{RMD})

$$\mu_{IMD} > \mu_{RMD} - \delta$$

where δ is the non-inferiority margin.

The non-inferiority margin determination follows the guidelines of Flight & Julious (2016). The non-inferiority margin is defined to be the clinical acceptable difference allowing us to conclude that there is no difference between the treatments. We will base our reflexion on SRT benefit from the validation of the RMD to satisfy the following requirements:

- Assay sensitivity, the RMD should provide a benefit over the unaided condition. This can be verified by the achieved mean benefit of +4 dB SNR (SD = 0.8 dB SNR).
- Constancy assumptions, the IMD will be tested in the same conditions and the eligibility criteria are similar between both studies.
- Minimized bias, to reduce the influence of results variability from natural fluctuation the difference between conditions is used rather than absolute SRT results.

From the reference study, a significant and audible difference could be found between the tested devices. This was also reflected by a difference of 1.3 dB SNR (SD = 1.6 dB SNR) in the SRT scores. The OLSA test manufacturer states that the precision to determine the SRT lies around 1 dB for within subject measures. We can therefore set the non-inferiority margin to 1 dB SNR which correspond to a little bit less than 80 % of an audible effect measured with the test. With a non-inferiority margin of 1 dB, we are still ensuring that the IMD has a positive effect over the unaided condition.

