11.4 Planned Analyses

The analysis and documentation will be done by the statistician using R (version 3.4) a statistical software package. R “stats” package will be used for the confidence interval, non-inferiority, and Wilcoxon tests. Documentation of the analysis will be done with R Studio under R Markdown format.

Main outcome: speech reception threshold (SRT from OLSA and GÖSA)

SRTs from the OLSA test are measured during the second visit. OLSA data from a previous trial (BF001-1611) are used for the hypothesis definition, the non-inferiority margin, and the sample size calculation.

The rationale for the analysis is: paired t-tests usually test that the mean differences are zero. The non-inferiority test compares the difference to a non-zero quantity δ . The assumptions of the paired t-test are:

1. The data are continuous (not discrete).
2. The data, i.e., the differences for the matched-pairs, follow a normal probability distribution.
3. The sample of pairs is a simple random sample from its population. Everyone in the population has an equal probability of being selected in the sample.

SRTs from the GÖSA test are measured during the third visit. The GÖSA speech material is different than the OLSA, because it uses different vocabulary and presentation levels. The GÖSA contains short everyday sentences while the OLSA uses standardized, meaningless sentences. Collecting data from two different speech materials should help to generalize our findings. However, due to different test properties (Kollmeier et al., 2011), a separate analysis must be conducted with each test. As we don’t have reference data for the GÖSA test, we cannot compute a non-inferiority margin.. Therefore, the GÖSA analysis is planned as a secondary analysis and described in section 11.4.3.

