11.4.2 Primary Analysis

Speech Reception Threshold (SRT) from the OLSA test will be measured under three test conditions: unaided, control (RMD), and test (IMD). Test condition order will be randomized using a Latin square design to control any potential order effect. The difference between control and test condition will be

compared to the non-inferiority margin to test for non-inferiority. The unaided condition will be used as control of the investigational device benefit if non-inferiority could not be shown.

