11.5 Handling of missing data and drop-outs

For missing data, the PI will contact the involved subject to evaluate the possibility of getting missing data from a questionnaire by post. If a test subject cannot come to the evaluation visit, after exhausting all the possibilities to reschedule a new one, the devices will be sent back per post. If a subject does not want to adhere to the protocol, he can easily switch back to his own devices and return the IMD.

Dropouts will not be replaced; therefore, extra subjects over the calculated sample amount will be included from the beginning to ensure enough completed cases with all data.

The analysis and report will include two separate sections. The first section is based on data from all recruited subjects (as the intention to treat ITT part) and the second section is based on the data from subjects that complete the entire protocol (per protocol PP). Demographical and audiological data (e.g. hearing loss thresholds, degree, and classification) will be available from all recruited subjects including the withdrawn subjects and will be analysed in the report.

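### Section 11.2's 16 subjects give 77%, not 80%, power for the planned paired t-test, and the synopsis allows 15 subjects and an exploratory analysis only

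*Protocol*

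**What the plan says.** **Aim and test.** Section 11.1 says that "the tested hypothesis should therefore focus on the non-inferiority of the IMD compared to the RMD", with stated null and alternative hypotheses and a 1 dB margin. Section 11.4.2 says that the difference between the two aided conditions will be "compared to the non-inferiority margin to test for non-inferiority". Section 11.4 identifies the procedure by a list headed "The assumptions of the paired t-test are", and explains that the usual zero difference is replaced by the margin.

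**Size.** Section 11.2 uses a one-sample formula with normal quantiles, SD 1.6 dB, margin 1 dB, alpha 0.05 and power 0.8, and concludes: "we will need a sample size of 16 to satisfy the test hypothesis".

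**Elsewhere.**
- Synopsis, Number of Participants with Rationale: "There will be an exploratory analysis of the data only. The total number of participants will be approximately 15-20".
- Section 6.1: "The exploratory study is based on a population of approximately 20 hearing impaired people".
- Section 7.4 describes back-up "test participants on the list to replace those that withdraw or are withdrawn".
- Section 11.5: "Dropouts will not be replaced; therefore, extra subjects over the calculated sample amount will be included from the beginning".

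**The concern.** The formula in 11.2 treats the SD as known. The paired t-test estimates it from the sample, and with about 15 degrees of freedom that costs some power, so the stated 80% does not belong to the stated test at the stated size.

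Three inconsistencies add to this:

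1. **Minimum number.** The lower end of the synopsis range is below the number that 11.2 requires, and it leaves no room for the surplus that 11.5 promises.
2. **Status of the analysis.** A reader of the synopsis would take the OLSA result as descriptive. A reader of section 11 would take it as a confirmatory non-inferiority conclusion. Section 4.1 presents the study as the final validation before the device is released for sale, so this status should be settled before data are seen.
3. **Replacement.** Sections 7.4 and 11.5 give opposite rules. They lead to different enrolment totals for the same completer target, and it is unclear how that target is secured.

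**Working it through.** **Inputs**
- SD of the paired difference 1.6 dB and margin 1 dB (sections 11.1 and 11.2).
- Alpha 0.05, one-sided, because the formula in 11.2 uses the quantile at 1 − alpha; target power 0.80 (section 11.2).
- True difference 0, implied because the formula divides by the margin alone. Section 8.1.1 also expects equal performance.
- Paired design (section 11.2) and paired t-test against the margin (section 11.4).

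**Step 1: reproduce the plan's figure.**
n = [1.6 × (1.645 + 0.842) / 1]² = 15.83, rounded up to 16. Power on the same normal basis is Φ(√n/1.6 − 1.645). At n = 16 this is Φ(2.5 − 1.645) = 80.4%. The stated 16 reproduces.

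**Step 2: power of the planned test.**
For the one-sided paired t-test, power = 1 − F(t), where t is the 0.95 quantile of the t distribution with n − 1 degrees of freedom. F is the noncentral t distribution function with n − 1 degrees of freedom and noncentrality √n × 1/1.6. At n = 16 the critical value is 1.753 and the noncentrality is 4/1.6 = 2.5, which gives 77.0%.

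| Completers | Normal formula | Exact paired t |
|---|---|---|
| 14 | 75.6% | 71.5% |
| 15 | 78.1% | 74.4% |
| 16 | 80.4% | 77.0% |
| 17 | 82.4% | 79.4% |
| 18 | 84.3% | 81.6% |
| 19 | 86.0% | 83.5% |
| 20 | 87.5% | 85.3% |

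Simulation with 400,000 runs per size agrees: 74.5%, 77.1%, 79.4%, 81.6% and 85.3% at 15, 16, 17, 18 and 20.

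**Step 3: sensitivity to the SD.** Exact t power at 16 completers is 90.1% for SD 1.3, 81.6% for 1.5, 77.0% for 1.6 and 72.6% for 1.7.

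**Step 4: compare the sections.**

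| Point | One statement | Conflicting statement |
|---|---|---|
| Number | 11.2: 16; 11.5: more than the calculated number from the start | Synopsis: as few as 15 |
| Purpose | 11.1, 11.2, 11.4.2: powered non-inferiority test | Synopsis: exploratory only; 6.1: exploratory study |
| Withdrawals | 7.4: replaced from back-ups | 11.5: not replaced |

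Sections 11.3 and 11.4.1 name the per-protocol set, so completers are the count that matters. Fifteen enrolled with one dropout leaves 14, and 71.5% power.

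**The case against.** **The power gap is small.** Normal quantiles are a common approximation, and 16 is not an arithmetic error. The shortfall is 3 points, or 2 completers, which is less than the uncertainty in the planning SD: with SD 1.5 instead of 1.6, power at 16 is 81.6%. This stands. Taken alone, the t-test point would be minor.

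**More than 16 are already planned.** Section 11.5 promises extra subjects and 6.1 gives about 20, so 16 reads as a completer target and the 15-subject case would not arise if 11.5 is followed. This is fair as a description of intent. It does not remove the synopsis figure, which permits what 11.5 rules out.

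**The exploratory label in 6.1 is loose wording.** Section 5.1 and section 11 leave no real doubt that a non-inferiority test is meant. That is a reasonable reading of 6.1, but the synopsis says the analysis is exploratory only, and that cannot be reconciled with section 11.

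**Back-ups may only describe usual site practice,** and either rule could support the completer count. The effect on power is small, but the two rules still contradict each other.

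**Eighteen may not be enough.** Section 11.4.3 cites a rule based on a 95% confidence interval. If that interval is two-sided and also decides non-inferiority, the one-sided level is 0.025. Exact t power is then 64.7% at 16 and 75.5% at 20, and 23 completers are needed for 80%. Section 11.2 uses one-sided 0.05, so this does not alter the finding, but the figure of 18 depends on that level.

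**Conclusion.** The concern holds. With the protocol's own inputs, 16 completers give 77.0% power for the planned test, and 18 are needed to pass 80%. Seventeen come close, at 79.4%. The shortfall is covered if at least 18 of the approximately 20 in section 6.1 complete. It is not covered at the synopsis minimum, where power is below 80% even on the protocol's own formula.

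These figures assume SD 1.6 dB, a true difference of 0 and a one-sided 0.05 test. The three contradictions, on minimum number, status of the analysis and replacement, need no assumptions and carry most of the weight. The point should be fixed, but it does not undermine the design.

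**What to change.** - **Section 11.2:** either restate power as about 77% for 16 completers (paired t-test, SD 1.6 dB, one-sided 0.05), or set the target at 18 completers for about 82%.
- **Synopsis, number of participants:** replace the 15 to 20 range with the approximately 20 of section 6.1, and in no case a number below that in 11.2, so that it agrees with 11.5.
- **Synopsis and section 6.1:** do not describe the primary OLSA non-inferiority test as exploratory. Keep that term for the GÖSA analysis, as section 11.4.3 does.
- **Sections 7.4 and 11.5:** reconcile them to a single replacement rule. Without replacement, 20 enrolled and 18 completers allows for 20 − 18 = 2 dropouts. If back-ups are used, say that they count toward the completer number.

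The cost is wording in four places: 11.2, the synopsis, 6.1, and either 7.4 or 11.5. No subjects are needed beyond the approximately 20 already planned.

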11.3 Statistical criteria of termination of trial

A single statistical analysis is planned once all recruited subjects have completed the trial (per-protocol). No interim analysis is planned and no “stopping rules” are set from a statistical perspective. PI’s and clinician judgement are considered as reliable enough to stop the trial.

11.4 Planned Analyses

The analysis and documentation will be done by the statistician using R (version 3.4) a statistical software package. R “stats” package will be used for the confidence interval, non-inferiority, and Wilcoxon tests. Documentation of the analysis will be done with R Studio under R Markdown format.

Main outcome: speech reception threshold (SRT from OLSA and GÖSA)

SRTs from the OLSA test are measured during the second visit. OLSA data from a previous trial (BF001-1611) are used for the hypothesis definition, the non-inferiority margin, and the sample size calculation.

The rationale for the analysis is: paired t-tests usually test that the mean differences are zero. The non-inferiority test compares the difference to a non-zero quantity δ . The assumptions of the paired t-test are:

1. The data are continuous (not discrete).
2. The data, i.e., the differences for the matched-pairs, follow a normal probability distribution.
3. The sample of pairs is a simple random sample from its population. Everyone in the population has an equal probability of being selected in the sample.

SRTs from the GÖSA test are measured during the third visit. The GÖSA speech material is different than the OLSA, because it uses different vocabulary and presentation levels. The GÖSA contains short everyday sentences while the OLSA uses standardized, meaningless sentences. Collecting data from two different speech materials should help to generalize our findings. However, due to different test properties (Kollmeier et al., 2011), a separate analysis must be conducted with each test. As we don’t have reference data for the GÖSA test, we cannot compute a non-inferiority margin.. Therefore, the GÖSA analysis is planned as a secondary analysis and described in section 11.4.3.

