6.2 Methods of minimising bias

6.2.1 Randomisation

A single group assignment to the IMD will be used. The test order will be randomized based on list created by the statistician. This means that for the speech tests the subjects will be randomized by the condition. This reduces bias by using a different starting and ending condition as the last condition has a higher chance of scoring higher due to a learning effect from the speech test. The list will not be concealed, but should be in the ISF so that the PI knows in which condition order to test each subject.

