7.3 Assignment to study groups

For the field tests the allocation is single group; therefore, all the test subjects will be assigned to the same group. The initial field test will be with the RMD and the second with the IMD, as it will take time

to have the IMD made by the lab.

For the lab tests the assignment to the test condition order will be randomized by the statistician. The test condition order will be randomized using a latin square design. This will minimize bias created when one test condition is tested in the final or last position all the time.

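### Condition order is randomised because a learning effect is expected, but the primary paired t-test has no position term; adding one is an optional, cheap gain in efficiency

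*Protocol*

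**What the plan says.** Section 6.2.1 gives the reason for randomising the order of conditions: "the last condition has a higher chance of scoring higher due to a learning effect from the speech test". Section 7.3 names the method, "The test condition order will be randomized using a latin square design", and section 11.4.2 repeats it for the primary OLSA test: "Test condition order will be randomized using a Latin square design to control any potential order effect".

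Section 11.4 sets out the test itself: "The rationale for the analysis is: paired t-tests usually test that the mean differences are zero". The non-inferiority version compares the mean difference with the margin instead of zero. Among its stated assumptions is that the matched-pair differences follow a normal distribution. Section 11.4.2 then compares the RMD-IMD difference with the margin. Neither section includes a term for position, period or sequence. The only covariables named are hearing loss degree and age, post hoc, in section 11.4.3.

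Section 11.1 explains the use of differences: "to reduce the influence of results variability from natural fluctuation the difference between conditions is used rather than absolute SRT results". The SD used for planning comes from the same section: "This was also reflected by a difference of 1.3 dB SNR (SD = 1.6 dB SNR) in the SRT scores". From it, section 11.2 concludes "we will need a sample size of 16 to satisfy the test hypothesis".

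**The concern.** The protocol predicts a nuisance effect and designs for it, but does not use the design in the primary analysis. Taking within-subject differences does not remove learning, because IMD and RMD are tested at different positions in every subject. Each paired difference therefore carries a learning component whose size and sign depend on the order that the subject received.

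If that component is left in the residual, the estimated standard error is too large for the precision actually achieved. The test rejects less often than its nominal level allows, and it has less power than the same data could give. With a calculated sample size of 16, a few points of power are worth having if they cost almost nothing.

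**Working it through.** **Inputs from the protocol.** Margin 1 dB, SD 1.6 dB, alpha 0.05 (one-sided, since the formula uses z at 1−α), power 0.80 (sections 11.1 and 11.2). Enrolment is about 15 to 20 (synopsis) or about 20 (section 6.1). Section 11.5 adds extra subjects from the start and gives no dropout rate.

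**Assumed.** Learning is linear at L dB per position, with L from 0 to 0.5. The value 0.5 means 1 dB from first to last test and is an upper case.

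**The protocol's own figure.** n = (1.6 × (1.645 + 0.842) / 1)² = 15.83, so 16. This reproduces section 11.2. The formula is a normal approximation; the t-test itself (noncentral t) has 77.0% power at n = 16 with no learning.

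**Variance added by learning.** Write D = SRT(RMD) − SRT(IMD), which equals the IMD benefit minus the RMD benefit, and d = IMD position minus RMD position. If each later position lowers the SRT by L, then D = true difference + L·d + error.

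- Cyclic 3×3 square: d is +1, +1, −2 (or the reverse signs). Mean 0, variance (1 + 1 + 4)/3 = 2.
- All six orders: d is +1, +1, −1, −1, +2, −2. Mean 0, variance (4 × 1 + 2 × 4)/6 = 2.

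The variance of D across subjects therefore rises by 2L². At L = 0.25 this is 0.125, or 4.9% of 1.6² = 2.56. At L = 0.5 it is 0.5, or 19.5%.

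**Why this gives no bias.** With balanced orders d averages zero, so the mean of D is unaffected. At n = 16, which is not a multiple of 3, a cyclic allocation is out of balance by at most 2/16 = 0.125 positions. That shifts the estimate by 0.125 × 0.5 = 0.06 dB at L = 0.5. Balance also keeps learning out of the true sampling variance of the mean, but not out of the estimated standard error. The unadjusted test is therefore conservative.

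**Simulation.** 100,000 runs per cell; permuted blocks; three or six orders (ranges cover both); true difference 0 for power and −1 dB for type I error. Unadjusted is the paired t-test on n−1 df. Adjusted is the intercept from regressing D on d, on n−2 df. The protocol does not say whether the 1.6 dB SD already contains position variance, so both cases are shown.

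| Power, unadjusted → adjusted | n = 15 | n = 16 | n = 18 | n = 20 |
|---|---|---|---|---|
| L = 0 (noncentral t) | 74.4 → 74.1% | 77.0 → 76.8% | 81.6 → 81.4% | 85.3 → 85.1% |
| L = 0.25, SD excludes position | 73.0 → 73.9–74.2% | 75.6 → 76.5–76.6% | 80.2–80.3 → 81.1–81.2% | 84.3–84.5 → 85.2% |
| L = 0.5, SD excludes position | 68.6 → 74.0–74.1% | 71.5–71.6 → 76.6–76.7% | 76.8–77.1 → 81.4–81.5% | 81.0–81.1 → 85.1–85.2% |
| L = 0.5, SD includes position | 75.9–76.1 → 81.6–81.8% | 78.8–78.9 → 84.2–84.3% | 83.6–83.7 → 88.1% | 87.1–87.4 → 90.9–91.2% |

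Type I error of the unadjusted test is 0.045–0.047 at L = 0.25 and 0.032–0.039 at L = 0.5. The adjusted test stays at 0.048–0.051 in both.

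Over both SD cases the gain is 0.7–1.2 points at L = 0.25 and 3.8–5.7 points at L = 0.5. With no learning the simulated cost is 0.1–0.7 points. Break-even is at about L = 0.1 to 0.15 dB.

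**The case against.** The strongest objection is that nothing in the protocol is wrong. It names a learning effect and answers it by design, and a balanced order followed by a paired t-test is coherent. The sentence in section 11.4 is correct as it stands, and a position covariate is the sort of detail that a statistical analysis plan may add. Most of this stands: the point is not a defect. It remains worth raising because section 11.4 does not leave the test open. It names the test, its assumptions and the software, so the comment concerns a stated choice. If the analysis plan already contains a position term, the point falls away.

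The second objection is that the benefit depends on an effect that the protocol does not size. This also stands. Below about 0.1 dB per position the term gains nothing, and the larger gains belong to the upper case.

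Third, if the 1.6 dB already contains order variance, the planned test loses nothing against plan: at n = 16 and L = 0.5 it has about 79% power, against 77.0% with no learning. That is correct. In that case the loss exists only relative to the adjusted test.

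Finally, the extra subjects absorb most of the loss. At 20 subjects the unadjusted test keeps about 81% even in the least favourable case, above the 80% target.

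**Conclusion.** The point holds as an optional improvement in efficiency. The planned test is valid, unbiased under balanced orders, and conservative when learning is present. Leaving out position costs about 1 point of power at L = 0.25 dB and about 4 to 6 points at L = 0.5 dB. It matters most near 16 completers and little at 20. The size rests on two things that the protocol does not give: the learning effect per position, taken here as linear and at most 0.5 dB, and whether the 1.6 dB SD already includes position variance.

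**What to change.** In section 11.4.2, keep the alpha of 0.05 and the 1 dB margin. For each subject compute D = SRT(RMD) − SRT(IMD). Regress D on the signed position difference (IMD position minus RMD position, so that zero means equal position), and test whether the intercept exceeds −1 dB on n−2 degrees of freedom. The R stats package named in section 11.4 can fit this.

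Two cautions on the form of the adjustment:

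- Do not replace the signed position difference by a plain before/after code. In a three-order cyclic square that shifts the intercept by about −L/2 (simulated: −0.25 dB at L = 0.5).
- Do not use a three-condition model with one pooled residual variance. Section 11.1 gives an SD of 0.8 dB for the RMD benefit over unaided and 1.6 dB for a device difference in the reference study. With those two variances (0.64 and 2.56) and an assumed unaided-IMD variance of 1.2, 2.56 or 4.0, simulated type I error at n = 18 was 0.108, 0.079 or 0.058 (20,000 runs, L = 0). The paired-difference regression gave 0.051 to 0.052. This caution depends on the assumed third variance and on carrying the reference-study SDs over to this trial.

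The cost is one covariate, one degree of freedom, and 0.1 to 0.7 points of power if there is no learning. Subjects, visits and the order list do not change.
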